6.9 Human Subjects/Ethical Considerations

All patients participating in the Prevention for Positives study component will be administered the Patient Survey, regardless of whether or not they are randomized to the CARE+/ACASI intervention. Individual-level data will be analyzed. This component is human subjects research. Written informed consent will be obtained from participants at the time of consenting for participation in the Prevention for Positives study component.

Providers from participating HIV care sites will be invited to complete a Web-based survey regarding their knowledge, attitudes and practices concerning ART for treatment, frequency of HIV testing, and limited sociodemographic information. The survey will be anonymous, and will collect no identifying information. This component is public health research. Informed consent will be obtained from the provider's completing the survey. Before the survey will display, providers will read the consent and if they agree to participate, will indicate their agreement by clicking a button labeled "I agree."

The protocol and supporting study materials (the informed consent form and any advertising materials) will be submitted to appropriate IRBs (a central and/or local site IRBs) for ethical review prior to study initiation. Any subsequent modifications to these materials will be submitted to appropriate IRBs, and, at a minimum, they will be submitted annually for continuing review and approval by these same ethics boards.

Written informed consent (or a mark for those who are illiterate, which will be witnessed by a third party) will be obtained from each study participant willing to complete the patient survey prior to study enrollment. The informed consent for the survey is incorporated into the consent form for the Prevention for Positives component. Each study site is responsible for developing an informed consent form for local use for the patient survey, based on the template provided with the protocol, that describes the purpose of the survey, the survey procedures, and the risks and benefits of participation, in accordance with all applicable regulations. Participants completing the patient survey will be provided with a copy of their informed consent form if they wish to receive it.

No physical or psychosocial risks are anticipated from participation in the patient or provider surveys as they involve no invasive procedures or reports of illegal or socially stigmatized behaviors. Further, all data will be anonymized once merged into the study database, and no names will be used in publications.

A small incentive will be provided to survey participants, both providers and patients, to compensate them for their time. For the patients, this compensation is included in

the incentive they receive for participating in the Prevention for Positives component of the study.

For patient surveys, all study-related information will be stored securely at the study site in areas with access limited to study staff. To maintain participant confidentiality, a coded number will identify all study data and administrative forms. All local databases will be secured with password-protected access systems. Forms, lists, logbooks, appointment books and any other listings that link participant ID numbers to other identifying information will be stored in a separate area with limited access. Survey information will not be released without the written permission of the participant, except as necessary to: authorized medical care providers; monitors of the NIAID and/or its contractors; representatives of the HPTN CORE and/or the SDMC; other government and regulatory authorities; and/or the site IRB.

6.10 Safety Monitoring and Adverse Event Reporting

The study team will not collect or report Adverse Events because there is no biomedical intervention. However, the team will collect and report all social harms that are brought to the attention of study staff members, using a study-specific incident report form. This form will be anonymous and will query common social harms such as altered personal relationships, forced change in housing, and physical violence. The form will also include space for a written narrative to document additional details of any social harm experienced. All research staff will be trained to properly complete the form. As a part of study training, research staff will also be trained on the provision of referrals to counseling and social service support. Reports of social harms will be reviewed quarterly or more often, if indicated, and reported to the medical officer together with any actions that are taken. Social harms will be summarized and reported to appropriate IRB(s) on an annual basis.

7.0 HIV SURVEILLANCE, ROUTINELY-COLLECTED AND OTHER SURVEY DATA

Use of HIV case and behavioral surveillance data and HIV testing data will be used for site selection in intervention communities and for process and outcome measures. Other data, including site provided data, may be utilized for these purposes in certain circumstances.

We will assess completeness, accuracy, timeliness and performance of the surveillance and any other data.

7.1 HIV Testing Data

HIV testing data will be used to select HIV test sites for randomization to the intervention vs. SOC arm, and as a process measure for the testing intervention in ED and inpatient facilities (Table 5). For selection of HIV test sites for interventions, information on HIV testing is available for HIV test sites that are publicly supported through federal funds in each of the six communities included in this study; additional data are available for other

HIV test sites supported in some local jurisdictions, such as NYC's AIDS Institute Reporting System. This includes the majority of HIV testing conducted by CBOs.

Data Sources and Definitions						
Information needed Description		Data source	Variables			
HIV Testing Data						
Site selection, intervention communities						
Volume of testing	Number of persons tested in XX year, by testing site	Local PEMS, local testing data	Name of testing facility, testing date			
	Number of new diagnoses, by testing site	HIV surveillance data	Name of facility of diagnosis, date of diagnosis			
	Where available, number of case reports to surveillance, by testing site	HIV surveillance data	Name of facility of diagnosis, date of diagnosis			
Process mea	sures for HIV testing interven	tions, intervention (communities			
Number of persons eligible	Number of persons eligible	Project specific collection at intervention sites	Data may or may not already be collected at selected sites. If not collected, collection will be implemented for this study			
Number of persons tested	Number of persons tested	Project specific collection at intervention sites	Data may or may not already be collected at selected sites. If not collected, collection will be implemented for this study			
Number of new diagnoses	Number of new diagnoses	HIV surveillance data, and project specific collection at intervention sites	Surveillance data: name of testing facility, testing data. Data may or may not be collected by selected sites, and if not collected, can be implemented at site or use surveillance data.			
	HIV Surveillance	e Data				
	Outcome Meas	ures				
Number/proportion of persons newly diagnosed who entered care, by site CD4 or VL within 3 months of diagnosis (CD4/VL date not equal to diagnosis date), by site		HIV surveillance data	HIV diagnosis date, name of testing site, VL date, VL result, CD4 date, CD4 result, demographics (DOB, sex, race/ethnicity, transmission category)			

 Table 5.
 Data Sources and Definitions

Data Sources and Definitions				
Information needed	Description	Data source	Variables	
Number/proportion of previously diagnosed persons not in care entered into care, by site	CD4 or VL within 3 months of diagnostic test, among persons with previous diagnostic test and no CD4/VL within the past year, by site	HIV surveillance data	HIV diagnosis date, name of testing site, VL date, VL result, CD4 date, CD4 result, demographics (DOB, sex, race/ethnicity, transmission category)	
VL suppression	Probability of undetectable VL amongst people established in care with previous VL/CD4, by site	HIV surveillance data	Name of treatment site, VL date, VL result, CD4 date, CD4 result, demographics (DOB, sex, race/ethnicity, transmission category)	
	Behavioral Da	ata		
Number/proportion of persons who had an HIV test in the past 12 months	See BRFSS 2009 questionnaire: 20.1 Have you ever been tested for HIV? Do not count tests you may have had as part of a blood donation. Include testing fluid from your mouth. (213) 1 Yes 2 No [Go to Q20.5] 7 Don't know / Not sure [Go to Q20.5] 9 Refused [Go to Q20.5] 20.2 Not including blood donations, in what month and year was your last HIV test? http://www.cdc.gov/brfss/qu estionnaires/pdf- ques/2009brfss.pdf	Local surveys (see descriptions below)	Testing, testing date	
Special HPTN 065 emphasis population: number/proportion of MSM who had an HIV test in the past 12 months	NHBS questions	National HIV Behavioral Surveillance (NHBS) system	Testing, testing date	

The CDC has developed a data entry and reporting system, the PEMS, to strengthen monitoring and evaluation of HIV prevention programs. PEMS is used by health departments and CBOs funded through CDC HIV-prevention cooperative agreements. PEMS allows grantees to collect agency data, community planning data, program plan data, and client-level data. This assures a comprehensive set of standardized variables are available.

The client-level data include information on testing site, client demographics, risk factors, test information and testing history. This allows a description, by site, of the number

tested and number positive, and a description of the population tested or positive. Additional variables that can be used to describe sites include agency characteristics (budget, sites, workers, contracts, network agencies), program plans (program models, target populations, interventions (CTR, Health Communications/Public Information Outreach, settings, sessions, activities), service delivery (service activities, recruitment, referrals), and community planning activities (target populations, priority interventions).

Some areas have testing report systems in addition to PEMS. For example, New York State collects testing data through the AIDS Institute Reporting System. Florida has PEMS data as well as a counseling and testing data base that includes all the variables needed to report an HIV case as well as testing history questions; these two data sources cover all clients tested in the public sector, *e.g.*, registered counseling and testing sites (AIDS Service Organizations (ASOs), CBOs, faith-based initiatives), and county health department clinics (STD, TB, Family planning, *etc.*).

Another testing measure for selection of intervention sites that can be derived from surveillance data is the number of new diagnoses by site.

Process measures (Table 5) to monitor testing at the testing intervention sites will be collected directly from the participating facilities.

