3.2 Design for Linkage-to-Care

The Linkage-to-Care component of the study is a two-arm, site-randomized, prospective, effectiveness clinical trial conducted within each intervention community. This study component compares the effectiveness of an FI intervention to link HIV-positive individuals from HIV test sites to HIV care sites with the usual SOC procedures. Each HIV test site will be randomized to either the intervention or SOC arm of the study. For this component of the study, study outcomes will be evaluated through routinely reported HIV surveillance data. Using surveillance data, study outcomes will continue to be evaluated for a period of one year after the FI intervention ends.

In order to identify the SOC for linkage, against which the incentives intervention will be assessed, an appropriate facility administrator will complete a brief survey that will collect key attributes of HIV testing sites, including types of navigation and support services already available to patients to facilitate linkage-to-care. Data will be collected from sites annually from 2009 - 2013.

For the purposes of this protocol, we consider an HIV-positive individual linked to care when that person has a VL or CD4 cell count assessment at an HIV care site within 3 months of confirmatory WB testing.

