3.6.3 Monitoring HIV Test Sites

It is possible that members of the intervention communities will learn of the FI to strengthen linkage-to-care and seek out HIV test sites offering these incentives. In all likelihood, the majority of individuals who seek testing will not know their HIV status yet and, thus, will be unaware that incentives are being offered for linkage-to-care. In addition, many of the HIV test sites in the study (~seven out of the 20 participating HIV test sites in each city) will be hospitals in which HIV testing will take place in emergency departments and inpatient units. Individuals seen in these settings are usually not there for the purpose of obtaining an HIV test. Thus, it is unlikely that these individuals will seek medical services based on the availability of FIs for linkage to HIV care.

However, it is possible that some individuals, who are aware of their HIV infection, may "recycle" through the HIV test sites due to the availability of FIs. There are some natural barriers to this phenomenon, as it is likely that the staff at these HIV test sites will recognize individuals who are testing with undue frequency. In these cases, staff may withhold the FI coupons from those who have already received them for a prior HIV-positive test. Another natural barrier is that individuals are known at HIV care sites, so individuals will be unable to re-link repeatedly to the same HIV care site. In addition, the FI intervention is designed such that multiple activities (lab-work and provider

interaction, both of which take time and effort) are required for the full redemption, which may discourage some from repeated linkage.

It should also be noted that based on the HIV prevalence in the intervention cities, relatively few people test positive out of all of those who test. Thus, the number of people who could "recycle" through the HIV test sites is relatively small compared to the total testing done in these venues.

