3.8.1.2 Endpoints for the Effectiveness of Linkage-to-Care

In this site-randomized design, Linkage-to-Care effectiveness endpoints will be evaluated for each site and intervention effectiveness assessed by comparing site outcomes for intervention vs. SOC sites.

The effectiveness endpoints for the Linkage-to-Care component of the study will be ascertained based on HIV surveillance data and will include the following:

- Proportion of HIV-positive individuals at each testing site, who either have a newly detected HIV infection (based on new surveillance case with confirmed WB) or who were previously diagnosed but were out of care (based on no VL or CD4 ascertainment in the year prior to a repeat WB test in an existing surveillance case), and who presently are linked to care as evidenced by having a CD4 cell count and/or VL measurement at a separate visit within three months of WB confirmation
- Mean time interval at each testing site from HIV diagnosis (WB confirmation) to first CD4 cell count or VL for those with newly detected HIV infection and those who were previously diagnosed but were out of care
- Proportion of HIV-positive individuals at a testing site (overall, and separately for those with newly detected HIV infection and those previously diagnosed who were out of care) with at least two CD4 cell count and VL measurements in the prior year

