3.8.2 Sample Size and Power

The primary endpoint of this study component is proportion of cases (newly diagnosed and previously diagnosed but not in care) with a CD4 cell count and/or VL measurement within three months of the diagnostic WB.

Randomization is by testing site, with balance achieved for baseline volume of testing and baseline linkage-to-care rates. Accrual of participants into the Linkage-to-Care

component of the study will occur over the first 24 months of the study, when eligible persons receive the FI coupon at an HIV test site randomized to the FI arm of the study. There will be no follow-up for this component of the study, other than the two visits in care (or a combined lab/provider intake visit).

In 2007, in the 20 testing sites with the highest volume in the Bronx, NY, 611 newly diagnosed HIV-infected people were identified. Of those, 77% were liked to care within three months, with linkage at different testing sites ranging from 30% to 100%. The mean number of newly diagnosed cases per provider in 2008 was 31, and ranged from five to 93. The intra-class correlation (ICC) of proportion linked to care in the Bronx was 0.27.

In 2008, in the 20 testing sites in Washington, D.C, the jurisdiction with the highest volume of people testing HIV-positive, 783 newly infected cases were identified. Of these, 67% were linked to care, ranging across different testing sites from 5% to 100%. The mean number of newly diagnosed cases per provider in 2008 was 40, and ranged from eight to 143. The ICC of proportion linked was 0.31.

These estimates do not include the population of those re-linking to care. It is anticipated that linkage success in SOC for this population will be lower because of the history of loss to care. We could reasonably expect that: 1) the number of people eligible for linkage-to-care will be higher because of longer study duration and addition of re-linked to care cases; 2) the proportion linked to care will be lower because of the re-linked to care cases; and, therefore, 3) the ICC will be smaller. It is assumed that the number of cases to be linked to care during the 24-month study duration will be similar to these past case loads on an annual basis. We will randomize 20 testing sites in each intervention city, and we expect to identify between 1200 and 2400 individuals for linkage-to-care, a mean of 60-120 people per testing site.

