3.8.4.1 Primary Effectiveness Analysis

The population for assessment of Linkage-to-Care is the following:

- 1. All individuals with newly detected HIV infections reported to the HIV surveillance system for the DOH jurisdiction of Washington, D.C. and the Bronx, NY who were tested at any of the 40 testing sites in the study
- 2. All participants eligible for re-linkage to care, defined as a WB recorded in the enhanced HIV/AIDS Reporting System (eHARs), at any of the 40 testing sites in the study after the implementation of FIs, who had no VL or CD4 assessment by a provider in the previous 12 months

The endpoint is the percentage of participants with a VL or CD4 cell count assessment within three months of the WB confirmation (separate from clinical assessment done at the time of the confirmation visit). Participants in the FI arm are attributed to the linkage-to-care strategy in place at the site where the first HIV-positive result was detected.

The estimation of intervention effect will test for a change in odds ratio of linkage-to-care between the SOC and FI test sites, assuming a correlation within participants tested at the same site, using Generalized Estimating Equations (GEE) methods.

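### The primary linkage-to-care endpoint is defined inconsistently, and its only operational form (Table 5) admits a later-day CD4 or viral load from the diagnosing admission while it can miss true linkages in D.C.

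*Protocol*

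**What the plan says.** The protocol states the linkage endpoint in five places.

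- Section 3.2 counts a person as linked who "has a VL or CD4 cell count assessment at an HIV care site within 3 months of confirmatory WB testing".
- Section 3.8.1.2, the endpoint list, asks for "having a CD4 cell count and/or VL measurement at a separate visit within three months of WB confirmation".
- Section 3.8.2, the power section, asks only for a "CD4 cell count and/or VL measurement within three months of the diagnostic WB".
- Section 3.8.4.1, the primary analysis, adds that the assessment must be "separate from clinical assessment done at the time of the confirmation visit".
- Section 7.1, Table 5, turns the outcome into surveillance variables. For new diagnoses the rule is "CD4 or VL within 3 months of diagnosis (CD4/VL date not equal to diagnosis date), by site". For people diagnosed earlier and out of care it is "CD4 or VL within 3 months of diagnostic test, among persons with previous diagnostic test and no CD4/VL within the past year, by site", with no exclusion by date, visit or place.

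The variables in both linkage rows of Table 5 are diagnosis date, testing site, CD4 and VL dates and results, and demographics. The outcome elements in Table 6 (section 7.2) are CD4 and VL results and dates and the facility of diagnosis. Neither lists where the linkage CD4 or VL was ordered. The viral suppression row of Table 5 does list the treatment site.

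Section 3.6.3 notes that "many of the HIV test sites in the study (~seven out of the 20 participating HIV test sites in each city) will be hospitals", with testing in emergency departments (EDs) and inpatient units.

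**The concern.** The definitions are not interchangeable, and the loosest sits where the data pull is specified. A patient found positive on admission may have CD4 or VL drawn a day or more later in the same stay. Under Table 5 that draw has a different date, falls inside three months, and scores as linked even if the patient never reaches an HIV care site. A coupon has no part in such a success, so it occurs alike in both arms. It pulls the difference toward zero and changes what linked means. For previously diagnosed people, Table 5 would count even a same-day draw.

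The date rule can also err the other way. Section 1.1.3.3 says that in D.C. any confirmatory testing needed is done at the first medical visit, with CD4 and VL taken then. A true linkage of that kind can carry the diagnosis date and be discarded, unless another CD4 or VL follows on a different date within three months.

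**Working it through.** **Step 1: two patients under each wording.** Patient A is diagnosed as an inpatient, has a CD4 drawn on a later day of the same stay, and never reaches a care site. Patient B is in D.C. and has the confirmatory Western blot, CD4 and VL together at the first care-site visit, with no further test within three months.

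| Place | Condition | Patient A | Patient B |
|---|---|---|---|
| 3.2 | at a care site | not linked, unless the hospital itself is taken as the care site | linked |
| 3.8.1.2 | separate visit | not linked, if the stay is one visit | not linked |
| 3.8.2 | three-month window only | linked | linked |
| 3.8.4.1 | apart from confirmation visit | not linked, if the stay is that visit | not linked |
| Table 5, new cases | different date | linked | not linked |
| Table 5, previously diagnosed | no exclusion | linked | linked |

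For these two patients, section 3.2 and the new-case row of Table 5 give opposite answers both times.

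**Step 2: exposure.** About 7 of 20 test sites per city are hospitals: 2 × 7 = 14 of 40, or 35% of sites. This is a share of sites, not of cases.

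**Step 3: the plan's own figures.** Table 2 in section 3.8.2 gives 37, 54 and 102 cases per site for 80% power at 67% versus 80%, with 20 sites per arm. These do not reproduce. No alpha is stated for this component, so two-sided 5% is assumed. With Table 2's own standard deviations (17% and 12% in the first row), the variance per pair of sites at 37 cases is (0.67 × 0.33 + 0.80 × 0.20)/37 + 0.17² + 0.12² = 0.0536. Then z = 0.13/√(0.0536/20) − 1.96 = 0.55, a power of about 71%; the other two rows give about 60% and 43%. That is a separate matter. Here it means only that dilution should not be expressed as a loss from 80% power.

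**Step 4: dilution.** Let f be the share of cases scored as linked automatically in both arms, and let the rest link at 67% and 80%. Then p0′ = f + (1 − f) × 0.67, p1′ = f + (1 − f) × 0.80, and the difference is (1 − f) × 13 points. The documents do not give f, so its values below are assumptions.

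| f | Standard of care | Incentive | Difference (points) | Odds ratio | Automatic share of standard-of-care successes |
|---|---|---|---|---|---|
| 0 | 67.0% | 80.0% | 13.0 | 1.97 | 0% |
| 5% | 68.65% | 81.0% | 12.4 | 1.95 | 7% |
| 10% | 70.3% | 82.0% | 11.7 | 1.92 | 14% |
| 20% | 73.6% | 84.0% | 10.4 | 1.88 | 27% |
| 35% | 78.55% | 87.0% | 8.5 | 1.83 | 45% |

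The last row is an outer illustration: hospitals supply 35% of cases, and every one of them, ED cases included, is automatic. With 100 cases per site and an intra-class correlation of 0.127, approximate power is 72.5% at f = 0, 69% at 5%, 66% at 10% and 60% at 20%.

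**Step 5: can the documents bound f?** Only loosely. Section 1.1.2.1 gives, for a national testing initiative, 1.4% of tests in inpatient settings and 34% in EDs. Section 1.3.3 gives inpatient positivity of 2.5% to 5% and an ED yield of 0.7% to 1%. The inpatient share of hospital positives is then between 1.4 × 2.5/(1.4 × 2.5 + 34 × 1.0) = 9% and 1.4 × 5/(1.4 × 5 + 34 × 0.7) = 23%. If hospitals supply 35% of cases, that is 3% to 8% of all cases, before asking how many have a later-day draw. But those figures predate the study, the inpatients were tested selectively, and the trial adds testing to admission orders, aiming at an 80% offer and 70% acceptance (section 2.8.2). The range is illustrative and is not an upper limit.

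**The case against.** The strongest reply is that Table 5 is a summary of data sources. The endpoint is set in 3.8.1.2 and 3.8.4.1, and with 3.2 these would, as worded, generally exclude a work-up during the same admission. Turning a separate visit into a rule on laboratory dates is ordinary work for a statistical analysis plan, which is not at hand. This stands in part: the defect is an unreconciled definition, not a settled rule that counts inpatient draws. But section 3.8.4 defers only secondary endpoints to that plan, whereas section 4.8.1.2 expressly defers the suppression algorithm, and the protocol's own statements still conflict.

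A reader might infer that the care-site condition cannot be applied because the facility is missing from the linkage rows. The documents do not support that. Section 3.6.3 expects surveillance to show a person linking to several different care sites, section 4.8.1.2 uses VL ordered at each site, and Table 5 draws the treatment site for suppression. Table 6 omits that variable too, so its silence does not show that the data are unavailable.

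A reader might also infer that a large share of successes is false, or that hospital sites sit near a ceiling. No passage gives the inpatient share of cases or the frequency of later-day draws, so neither claim has support. On the odds-ratio scale, which the primary analysis uses, the movement is small. Nothing here favours one arm.

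**Conclusion.** The point holds as an inconsistency in the primary endpoint that should be settled before linkage data are extracted. Table 5, taken literally, counts some people who never reached care and can miss some who did. The size is unknown because f is unknown. At an assumed f of 5% to 20%, a 13-point gain is seen as about 12.4 to 10.4 points and an odds ratio of 1.97 as about 1.95 to 1.88. This assumes an equal f in both arms and the full 13-point gain among the other cases. The D.C. error cannot be sized from the documents. The firmer harm is to the meaning of the endpoint; the loss of contrast is modest unless f is large.

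**What to change.** Use one definition in 3.2, 3.8.1.2, 3.8.2, 3.8.4.1 and both linkage rows of Table 5: a CD4 or VL within three months, ordered by an HIV care site or provider and not by the diagnosing ED or inpatient unit. Let this replace the date and visit exclusions, so that a test ordered by a care site on the day of confirmation still counts.

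Add the ordering facility to the linkage variables in Tables 5 and 6. Apply the rule at all test sites, to new and previously diagnosed cases, in both arms, and to the baseline linkage rates used to balance the randomization (3.4 and 3.8.3).

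The cost is small: one variable of a kind already used for the suppression outcome, plus wording. Hospital-based HIV clinics that share a facility code with the ward will need a mapping, backed by a sensitivity analysis of hospital versus non-hospital test sites.
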